### 1.3. Study Objective

The objective of this post-market clinical follow-up study is to evaluate the clinical outcomes of patients receiving PhotoFix as a patch within a vascular repair or reconstruction procedure.

## 2. DETAILED STATISTICAL METHODS

### 2.1. General Statistical Methods

All measured variables and derived parameters will be listed individually in an Excel spreadsheet listing and, if appropriate, tabulated by descriptive statistics. For descriptive statistics, summary tables will be provided. Sample size, frequency, and percentages will be presented for categorical variables. Sample size, arithmetic mean, standard deviation, median, minimum and maximum will be presented for continuous variables.

## **2.2. Study Population**

All consented patients will be included in the basic patient demographics summary; this section will include data collected on the Demographics Electronic Case Report Form (eCRF). All patients who receive PhotoFix as part of their vascular repair or reconstruction surgery will be considered enrolled and included in all additional summaries and analyses.

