3.2 Study Size & Duration

Patients will be enrolled at approximately 10 sites. The enrollment period will span the time needed to consent approximately 166 patients. The target sample size is 100; projected enrollment considers a screen failure rate of 33% and an early termination rate of 10%. Enrollment is estimated to take a minimum of 8 months from Institutional Review Board (IRB) approval and site activation. Enrollment will begin at the principal investigator's site and in agreement with all central and local IRB requirements. The enrollment period will continue until the Sponsor decides to stop enrollment. The Sponsor will activate additional sites at their discretion.

A singular anatomical region will be selected for patch use. More than one patch can be used within the repair or reconstruction of this target region. However, patients requiring patches at distinct anatomical regions will be excluded. Additionally, patients undergoing concomitant procedures requiring additional prosthetics (e.g. stents) will be excluded. For complex cases, where clarification on these criteria is required, the Sponsor should be contacted prior to obtaining consent.

Patients undergoing a vascular procedure which falls within the indications for use and requires the use of PhotoFix will be screened and consented for the study, pre-operatively.

The study will collect prospective data at 5 time points; data will be collected pre-operatively, intraoperatively/immediately post-operatively, 1 month post-operatively, 3 months post-operatively, and 6 months post-operatively. All study patients will be expected to participate in all study required evaluations. Patients will be expected to come into the office at the 3 follow-up visits, post hospital discharge. For all post-operative visits outside the hospital, a +/- 14 day window is allowed for schedule fluctuations, but visits should ideally remain at the intended intervals. Data will also be collected on any unscheduled events (i.e. reoperation, explants, etc.) which may occur during the study period.

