3.4.5 Intraoperative Evaluation

Patients that meet the study criteria will receive PhotoFix as a vascular patch, per the IFU. A patient will remain eligible for continuation if PhotoFix remains implanted at the conclusion of their vascular surgery; patients would be considered enrolled at this point. Peri-operative and post-operative (<24 hours after surgery) data will be collected on all enrolled patients; this data will be entered into the Operative Assessment eCRF (Appendix D). The following measures will be monitored and documented per indication, but may include:

- Surgery date
- Implanting surgeon
- Number of PhotoFix Patches Used
- PhotoFix lot number(s)
- PhotoFix patch size(s) (indicated on box(es))
- Patch implant site
- Surgical procedure description
- Concomitant procedure description
- Any adverse events, device malfunctions, or intraoperative mortality
- Peri-operative imaging data

Any intraoperative adverse events will be captured on the Adverse Event eCRF (Appendix D). Patients will be told to contact the investigator in the event of any complications which occur during the study. The contact information for the Principle Investigator is included in the copy of the signed ICF each consented patient will have received.

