6.7 Statistical Analysis Plan

Enrolled patients will be described in aggregate and by indication (as deemed appropriate); baseline characteristics will include, but not limited to, age, sex, race, ethnicity, body mass index (BMI), comorbidities, fundamental diagnosis/etiology, and pertinent surgical history. Operative details will be described in aggregate and include a summary of the types of procedures performed, by relevant category. Parameters with continuous data types will be summarized using descriptive statistics, i.e., mean, standard deviation, and range. Categorical clinical parameters will be summarized based on percentages.

Ipsilateral central neurologic event rate, overall survival, re-operation rate, explant rate, and restenosis rate ($\geq 50\%$ stenosis) will be summarized based on percentages of affected patients and included in a table, which will summarize the endpoints in aggregate and by surgical indication (ex. CAS, ESRD, PAD, AAA, etc.). The summary of ipsilateral central neurologic event rates will include all events (transient ischemic attack, amaurosis fugax, stroke, and symptomatic carotid occlusion), as well as the incidence of each event individually.

Additional analysis of follow-up data will also be performed with the Kaplan-Meier method, as deemed appropriate by the incidence of events. Kaplan-Meier plots may be generated for endpoints including overall survival, primary patency, secondary patency, as well as freedom from ipsilateral central neurologic event rate, re-operation, explant, and restenosis ($\geq 50\%$ stenosis). Kaplan-Meier plots for survival will include the following mortality classifications: all causes of mortality, vascular-related mortality and device-related mortality (as applicable). The remaining plots will be specific to indication, if the sample sizes allow for the creation of meaningful plots.

The incidence of adverse events will be categorized and summarized with percentages for the aggregate sample. Adverse events will be divided into early and late post-operative events to represent the distribution of occurrences. Events will be considered as early events if the event occurs <30 days after the operation, while late post-operative events will be considered to be all events happening after this time period. Early and late events will be presented by indication for surgery, seriousness of event, and relation to PhotoFix. Adverse events occurring secondary to

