## **2.4. Demographics and Patient Baseline Characteristics**

Patient demography will be presented using summary statistics (sample size, mean, standard deviation, median, minimum and maximum) for continuous measurements, or frequency tables (numbers and percentages) for categorical measurements.

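### SAP 2.2 bases the demographics summary on all consented patients, about a third of them expected screen failures, whereas Protocol 6.7 describes enrolled patients; the SAP requires no demographic summary of implanted patients alone

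*SAP*

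**What the plan says.** SAP 2.2 (Study Population) sets two populations. For demographics the rule is "All consented patients will be included in the basic patient demographics summary", and the source is the Demographics eCRF. Patients who receive PhotoFix in their surgery "will be considered enrolled and included in all additional summaries and analyses".

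SAP 2.4 (Demographics and Patient Baseline Characteristics) gives only the form of the summary: "Patient demography will be presented using summary statistics (sample size, mean, standard deviation, median, minimum and maximum) for continuous measurements", with frequency tables for categorical items. It names no population.

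Protocol 6.7 (Statistical Analysis Plan) starts from a different population: "Enrolled patients will be described in aggregate and by indication (as deemed appropriate"). The variables follow in the same sentence: "baseline characteristics will include, but not limited to, age, sex, race, ethnicity, body mass index (BMI"), then comorbidities, diagnosis and surgical history. Protocol 3.4.5 fixes when a patient becomes enrolled. The patch must still be in place when surgery ends, and "patients would be considered enrolled at this point".

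Protocol 3.2 gives the expected numbers: about 166 patients consented for a target of 100, where "projected enrollment considers a screen failure rate of 33% and an early termination rate of 10"%.

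**The concern.** The same variables have two populations in the two documents. The SAP is the one written to guide the interim and final reports (SAP 1.1), so a programmer would follow its rule. That rule uses the word additional for the summaries on implanted patients, so it sets the demographics summary apart from them, and SAP 2.4 does not bring it back.

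This is a single-arm study. With no comparator, a reader judges whom the event and patency results apply to from the description of the patients. If the demographics table includes a sizeable group who never received the device, its denominator will not match that of the outcome tables. Its age, sex, race, ethnicity and body-size figures will then be a blend of two groups. Screen failures are also not a random subset. They can be excluded for reasons such as cancer history, short life expectancy, recent stroke, or atrial fibrillation with carotid endarterectomy (Protocol 3.3.2), and some of these could plausibly be related to age or sex.

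**Working it through.** **Inputs.** From Protocol 3.2: target 100, screen failure 33%, early termination 10%, about 166 consented. From SAP 2.2: demographics on all consented, everything else on implanted. From Appendix D: the Demographics eCRF holds date of birth, sex, race, ethnicity, height and weight. From Protocol 3.4.3: the form is completed at screening. From Protocol 7: it is source-verified for screen failures, so these patients will have the data.

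**Step 1: reproduce the plan's 166.** Inflating for each loss in turn:
- enrolled needed = 100 / (1 − 0.10) = 111.1
- consented needed = 111.1 / (1 − 0.33) = 165.8, or 166 rounded up

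This matches the stated figure. On this reading, 100 is the number completing follow-up.

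**Step 2: make-up of the SAP 2.2 table.**
- screen failures: 166 × 0.33 = 54.8, about 55
- implanted: 166 × 0.67 = 111.2, about 111
- completing: 111.2 × 0.90 = 100.1, about 100

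So the demographics denominator is about 166 and the outcome denominator about 111. If the target of 100 is instead read as patients enrolled, the non-implanted number 166 − 100 = 66, or 66/166 = 40% of the table.

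**Step 3: effect on a reported figure.** Let s be the share of the table not implanted, and D the screen-failure value minus the implanted value of a mean or percentage. Then

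table value = (1 − s) × implanted + s × screen failure = implanted + s × D.

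The documents give no value for D, so the values below are assumptions that show the range (years for age, percentage points for a proportion).

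| D | Shift at s = 0.33 | Shift at s = 0.40 (66/166) |
|---|---|---|
| 0 | 0 | 0 |
| 3 | 1.0 | 1.2 |
| 5 | 1.7 | 2.0 |
| 10 | 3.3 | 4.0 |

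**Step 4: what is affected.** Only the Demographics eCRF fields fall under the consented-patient rule: age through date of birth, BMI through height and weight, and sex, race and ethnicity directly. Indication, symptom status, comorbidities, and surgical and social history are on other forms. Under SAP 2.2 they belong to the additional summaries on enrolled patients.

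**The case against.** The best reply is that the two documents can both be satisfied. Including every consented patient in a basic summary does not forbid a second summary of enrolled patients, and Protocol 6.7 already commits to one. The individual data are listed in full (SAP 2.1 and 2.21) and screen failures appear in the disposition table (SAP 2.3), so the enrolled-only figures can be produced at any time. No event rate or Kaplan-Meier curve depends on this table. All of that stands. It limits the consequence, but it does not supply the missing instruction: nothing in the SAP requires the enrolled-only table.

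Several stronger readings are tempting, and the documents do not support them:

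- A reader might infer that the baseline table will describe different people from the outcome tables. About two thirds of the people in it are the implanted patients, and most of the clinical case-mix is already on the enrolled set. For the same reason, demographics are not the sole basis for judging whom the results apply to.
- A reader might infer that the SAP rules out demographics by indication. SAP 2.3 and 2.8 allow subgroup summaries at discretion, and Protocol 6.7 carries a similar qualifier.
- A reader might infer that the reported figures will be distorted by a known amount. The direction and size of D are unknown, and D could be zero.
- A reader might infer that re-screened patients will be counted twice. Protocol 3.4.3 provides for reconsent, but neither document says that a second record is created, and SAP 2.2 counts patients. Double counting is possible but not established.

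**Conclusion.** The point holds as a conflict over population. SAP 2.2 states a rule for demographics that differs from Protocol 6.7, and SAP 2.4 does not resolve it. Followed as written, the SAP yields a demographics table in which about 55 of 166 people (33%) have no outcome data, and it requires no summary of the roughly 111 implanted patients alone. This rests on the plan's projected screen-failure rate and on reading 100 as completers; the share is 40% if 100 means enrolled. The resulting shift, about 0.33 × D, can be illustrated but not estimated from the documents. The issue is confined to the demographic fields of a descriptive table. It affects how readers characterise the treated patients, and leaves the endpoint results unchanged.

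**What to change.** In SAP 2.2 and 2.4, state that demographics are tabulated for enrolled (implanted) patients, in aggregate and by indication as deemed appropriate, in line with Protocol 6.7. Show consented-but-not-enrolled patients in a separate column, so that the information on screen failures is kept, and say that each person is counted once.

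The cost is one SAP sentence and one extra table column. No new data are needed, because the Demographics eCRF is already completed for everyone screened.

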## **2.3. Patient Indication, Disposition and Characteristics**

The number of patients with each surgical indication will be summarized. Subgroup summaries will be included, as deemed necessary, and based on the sample sizes and apparent differences between the patients.

Change in patient status, including, withdrawals, discontinuations, and screen failures, will be summarized in a disposition table for all subjects. Reasons for any discontinuation will also be categorized and summarized appropriately.

## **2.4. Demographics and Patient Baseline Characteristics**

Patient demography will be presented using summary statistics (sample size, mean, standard deviation, median, minimum and maximum) for continuous measurements, or frequency tables (numbers and percentages) for categorical measurements.

## **2.5. PhotoFix Patches**

The number of PhotoFix patches implanted during each surgery will be presented as frequency counts. Also, the average number of PhotoFix patches implanted will be summarized as a continuous outcome. The size of PhotoFix patches implanted, as indicated on the box, will be included as a summary table. The size of implanted PhotoFix patches will be described using summary statistics for continuous measurements (sample size, mean, standard deviation, median, minimum and maximum).

## **2.6. Operative Characteristics**

Operative details, including surgical description, concomitant procedure description, ability to detect patch sidedness, and patch implant technique, will be presented using frequency tables. Surgery descriptions will be manually categorized, as deemed appropriate. Concomitant surgical procedures will also be manually categorized, as deemed appropriate.

## **2.7. Concomitant Statins and Blood Thinners**

Medications will not be coded. Concomitant medications will be defined as any medication that stops on or after the day of consent. All medications will be presented in a data listing. Summary statistics of patients on statins and blood thinners will be presented individually, as numbers and percentages.

## 2.8. Study Evaluations

All summaries will be presented in aggregate; subgroup summaries, by indication, will be included, as deemed appropriate.

## 2.9. Definition of Analyses

All analyses will focus on outcomes reported during the follow-up period, after PhotoFix implant. Analyses will summarize data collected through the end of follow-up; analyses at each time point are not planned, unless otherwise indicated.

### 2.9.1 Primary Analysis

- (Carotid Endarterectomy Only)

#### **Incidence of Central Neurologic Events:**

- Percent of patients who experienced at least one transient ischemic attack
- Percent of patients who experienced at least one case of amaurosis fugax
- Percent of patients who experienced at least one stroke
- Percent of patients who experienced symptomatic carotid occlusion at least once
- Percent of patients who experienced any of the central neurologic events of interest at least once

- (All Non-Carotid Indications)

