6.1 Study Endpoints & Variables

In the case of CEAs, the primary endpoint of the study will be rate of ipsilateral central neurologic events.

- Ipsilateral central neurologic events: Transient ischemic attack, amaurosis fugax, stroke, and symptomatic carotid occlusion.

In the case of all other (non-CEA) vascular procedures, the primary endpoint of the study will be primary patency in the target artery or vein.

- Primary patency (of target vessel): Loss of patency will be determined by the loss of previously palpable pulses, patients presenting with recurrent symptoms, a drop in ABI >0.15 in the case of lower limb artery repair, Doppler ultrasound findings of occlusion, angiography of the affected vessel or a combination of these.

The secondary endpoints of the study will include: overall survival rate, all-cause reoperation rate, device-related reoperation rate, explant rate, restenosis rate, adverse event rate, and secondary patency (HAR only).

- Overall Survival:
 - Early mortality: Death < 30 days following PhotoFix implantation.
 - Late mortality: Death ≥ 30 days following PhotoFix implantation, until last day of follow-up.
- All-Cause Reoperation Rate: The total number of reoperations required in patients over the follow-up period, which include the repair or alteration of the surgical area around the patch.

- **Device-Related Reoperation Rate:** The total number of unplanned reoperations required in patients over the follow-up period, which are determined by the surgeon to be device-related.
- **Explant Rate:** The total number of device explants over the course of follow-up. Explants will include the removal of PhotoFix for any reason after implantation.
- **Restenosis Rate:** The total number of documented cases of stenosis documented as the recurrence of abnormal narrowing of a vessel after corrective surgery.
- **Adverse Event Rate:** The total number of any unfavorable and unintended sign (including an abnormal laboratory finding), symptom, or disease temporarily associated with the use of a device, whether or not related to the device.
- **Secondary Patency (HAR only):** The time from implantation to the point where the access is abandoned.

Statistical analysis will be used to assess all study endpoints as applicable.

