15. History of Transient Ischemic Attack (TIAs)	 0  1  2  3  \geq 4  Unknown
If \geq 1, indicate when the most recent TIA occurred.	/ / Month/Day/Year
16. History of radiation to patch site	 Yes  No  Unknown
17. Describe of other significant medical condition	 None
18. (AAA/CAS/HAR only) History of Peripheral Arterial Disease	 Yes  No  Unknown
19. (CEA only) History of contralateral disease	 Normal  $<$ 50%  50 – 70%  $>$ 70%  Unknown

Surgical History eCRF	
Study Subject ID	
1. History of any cardiovascular surgery	 Yes  No  Unknown
If yes, how many prior cardiovascular surgeries	
If yes, how would you classify the surgeries	 Cardiac  Vascular (select all that apply)
2. If yes, categorize the surgery (1) *List most recent first	 Open  Endoscopic  Unknown
If yes, describe surgery	
Date of surgery	/ / Month/Day/Year
3. If yes, categorize the surgery (2)	 Open  Endoscopic  Unknown
If yes, describe surgery	
Date of surgery	/ / Month/Day/Year
4. If yes, categorize the surgery (3)	 Open  Endoscopic  Unknown
If yes, describe surgery	
Date of surgery	/ / Month/Day/Year
5. If yes, categorize the surgery (4)	 Open  Endoscopic  Unknown
If yes, describe surgery	
Date of surgery	/ / Month/Day/Year

Social History eCRF	
Study Subject ID	
1. History of Tobacco Use	 None or none for last 10 years  None current, by smoked in last 10 years  Current (includes abstinence < 1 year), less than 1 pack/day  Current, ≥ 1 pack/day  Unknown

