5. Classify the event as one of the following (if multiple symptoms, classify by most severe)	 Amaurosis Fugax  Bleeding event  Cardiac event  Endoleak  Infection  Inflammation/Edema  Pain  Paraparesis  Renal event  Stroke  Symptomatic Carotid Occlusion  Thrombosis  Trauma  Transient Ischemic Attack  Other: _____
(Infection only), was a culture taken?	 Yes  No
(Infection only), If yes, what were the reported results?	 Inconclusive  Positive (identify organisms): _____  Negative  Report not available
6. Describe the Event	
7. Consequence of Adverse Event	 Surgical Intervention  Hospitalization (New or Prolonged)  Death  Other: _____  None

*Select all that apply

Adverse Event eCRF	
If death is indicated, provide cause of death	 Unknown
8. Required Drug Treatment *Update Medication eCRF, as applicable	 Yes  No  Unknown
9. Classify the Adverse Event. *Refer to Protocol Appendix E, Definitions	 Adverse Event (AE)  Unanticipated Adverse Effects (UAE)  Serious Adverse Event (SAE)
If SAE, select at least one of the following	 Death  Life Threatening  Other Medically Important Serious Event  Persistent/ Significant Disability  Requires or Prolongs Hospitalization *Select all that apply
10. Is the event related to the subject's vascular surgery?	 Yes  No
11. Is the Adverse Event related to PhotoFix?	 Definitely  Probably  Possibly  Unrelated

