### 1.2. Study Overview

This study is a post-market, prospective, multicenter study designed to evaluate the clinical outcomes of patients receiving PhotoFix® Decellularized Bovine Pericardium (PhotoFix) as a patch within a vascular repair or reconstruction procedure. A goal of 100 patients will be enrolled at approximately 10 sites.

The primary study endpoint for patients with carotid artery stenosis (CAS) undergoing carotid endarterectomies (CEA) will be rate of ipsilateral central neurologic events; the primary endpoint for all other vascular procedures will be primary patency. The secondary endpoints include overall survival, all-cause reoperation rate, device-related reoperation rate, explant rate, restenosis rate, adverse event rate, and secondary patency (hemodialysis access repair (HAR) only). Data will be collected at 5-time points: baseline (pre-operatively), intra-operatively, 1 month post-operatively, 3 months post-operatively, and 6 months post-operatively.

The investigation will be conducted for a period of time required to collect all follow-up, as needed on each patient, but no longer than 7 months after the patient's operation.

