#### **Primary Patency:**

- Time from PhotoFix implantation to the time when patency in the vessel is documented as lost
  - Loss of patency includes loss of previously palpable pulses, presentation of recurrent symptoms, a drop in ABI $>0.15$  in the case of lower limb artery repair, Doppler ultrasound findings of occlusion, angiography of the affected vessel or a combination of these.

Loss of patency will also be considered if an intervention to restore or maintain patency is documented. In the event that loss of patency is documented as “no” on the Follow-up eCRFs and evidence of an intervention involving patency restoration is reported on the Adverse Event eCRF, a query will be issued and resolved appropriately.

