## **2.10. Incidence of Central Neurologic Events**

Frequency counts and percentages will be presented in a table for enrolled patients who received PhotoFix during carotid endarterectomy (CEA).

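### The CEA primary endpoint is ipsilateral neurologic events, but the SAP's counting rules carry no side condition and the Adverse Event eCRF has no field for side

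*SAP*

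**What the plan says.** The endpoint is ipsilateral wherever it is named. Protocol 6.1 states that for CEA "the primary endpoint of the study will be rate of ipsilateral central neurologic events". SAP 1.2 repeats this for patients with carotid stenosis "undergoing carotid endarterectomies (CEA) will be rate of ipsilateral central neurologic events", and Protocol 1.2 agrees. Protocol 6.7 carries the condition into its analysis text ("The summary of ipsilateral central neurologic event rates will include all events") and also promises the incidence of each event type separately.

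The operative SAP text does not carry it. SAP 2.9.1 lists five percentages for CEA patients: one each for TIA, amaurosis fugax, stroke and symptomatic carotid occlusion, and a composite, "Percent of patients who experienced any of the central neurologic events of interest at least once". None mentions side. SAP 2.10 says only that counts and percentages will be tabulated for enrolled CEA patients.

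In Protocol Appendix D, the Medical History eCRF records the operated side (item 6: right, left or not applicable). The Adverse Event eCRF (items 1 to 13) records event type, dates, a free-text description, consequence, seriousness, relatedness and status, but no side or vascular territory.

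**The concern.** A programmer working from SAP 2.9.1 and 2.10 would count a stroke or TIA on either side. That is a different quantity from the one SAP 1.2 names as primary. The form that supplies the events gives no structured means of restricting the count, because the operated side is recorded and the event side is not.

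Contralateral events are foreseeable from the documents. Item 19 of the Medical History eCRF asks CEA patients about disease in the opposite carotid, with levels up to more than 70% stenosis, and Protocol 3.3.2 does not exclude such patients.

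Two outcomes are possible if nothing changes. Either events away from the patched side enter the headline rate and overstate it, or side is assigned at analysis, without a stated rule, by people who already know the outcomes. Both affect the primary result for CEA patients.

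**Working it through.** **The texts side by side**

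| Place | Side condition? |
|---|---|
| Protocol 1.2, 6.1 and 6.7 | Yes |
| SAP 1.2 | Yes |
| SAP 2.9.1, four component percentages | No |
| SAP 2.9.1, composite | No |
| SAP 2.10 | No |
| Medical History eCRF, item 6 | Operated side recorded |
| Adverse Event eCRF, items 1 to 13 | No event side or territory |
| Follow-Up eCRF, item 5 | Patency loss in the target vessel only |

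Protocol 6.1 lists four event types under the ipsilateral label without saying how side is judged. Appendix E does not define the term. The Follow-Up item may help to place an occlusion, but it does not give the side of a TIA, stroke or episode of amaurosis fugax.

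**Size**

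The documents state no CEA sample size, expected rate or precision for this endpoint, so there is no figure to reproduce. All inputs below are assumptions, with CEA numbers taken as 30, 50 or 70 of the target 100 patients.

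Let n be the number of CEA patients, a the number with at least one ipsilateral event, and c the number whose only neurologic events are not ipsilateral.

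- Rate as named: a/n
- Rate as SAP 2.9.1 counts it: (a + c)/n
- Difference: c/n, which is never negative

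A patient with events on both sides is already in a, so adds nothing. For c = 1 the difference is 100/30 = 3.3, 100/50 = 2.0 and 100/70 = 1.4 percentage points.

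With a = 1 and c = 1, and exact (Clopper-Pearson) 95% intervals:

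| n | Ipsilateral only | Any side |
|---|---|---|
| 30 | 1/30 = 3.3% (0.08 to 17.22) | 2/30 = 6.7% (0.82 to 22.07) |
| 50 | 1/50 = 2.0% (0.05 to 10.65) | 2/50 = 4.0% (0.49 to 13.71) |
| 70 | 1/70 = 1.4% (0.04 to 7.70) | 2/70 = 2.9% (0.35 to 9.94) |

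With c = 0 the two rules give the same rate.

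**A separate, smaller point**

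Item 5 of the Adverse Event eCRF asks for one category per event, the most severe where there are several symptoms. An occlusion that presents as a stroke may then be recorded only as a stroke, and be missing from the individual occlusion rate that Protocol 6.7 promises. The composite is not affected.

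**The case against.** The best defence is that SAP 2.9.1 is shorthand. SAP 1.2 has already named the endpoint as ipsilateral, the composite refers to events of interest, and the four event types match those listed under the ipsilateral label in Protocol 6.1. That reading is possible, but the phrase occurs only in the composite, and no counting rule in 2.9.1 or 2.10 refers back to the definition.

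Second, side is probably recoverable. Sites should send source notes with each adverse event (Protocol 4.3), queries can be raised (6.5), full source verification is intended (6.6 and 7), and the Adverse Event eCRF has a free-text description. This is a fair point: the information is unlikely to be lost. But nothing prompts sites to state side, and being able to find it does not make it a condition of the count.

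Third, the exclusions in Protocol 3.3.2 (atrial fibrillation in CEA patients, stroke within 3 months, thromboembolic disease) and follow-up of at most 7 months plausibly make non-ipsilateral events rarer. They do not rule them out.

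Fourth, the example is hypothetical, its intervals overlap heavily, and the study is single-arm and descriptive. All true, and this limits the consequence to the reported rate.

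One contrast should not be pressed far. For primary patency, SAP 2.9.1 does say that when forms disagree "a query will be issued and resolved appropriately". That shows cross-form reconciliation was considered for the other primary endpoint, but it does not name who decides either.

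**Conclusion.** The concern holds and should be fixed. The SAP names one quantity as the CEA primary endpoint and gives counting rules for a broader one, and the adverse event form does not collect the item needed to tell them apart.

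The error can only raise the reported rate, by 1/n for each patient whose only event is not ipsilateral: 1.4 to 3.3 percentage points per patient for an assumed 70 down to 30 CEA patients. With few events, one such patient could double the rate. If there are none, nothing changes. No hypothesis test, threshold or power calculation depends on this. The conclusion rests on the text of the two documents; only the size rests on assumed counts. The single-category point on item 5 is secondary and the conclusion does not depend on it.

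**What to change.** 1. In SAP 2.9.1 and 2.10, add *ipsilateral to the PhotoFix-patched carotid* to all five percentages and to the table description. Events in any territory can be reported as a supportive line.
2. On the Adverse Event eCRF, add one field for the four neurologic categories: ipsilateral to the patch, contralateral, vertebrobasilar, or undetermined. Match it to the operated side in Medical History item 6 and check it against the source notes. State who assigns it.
3. State in the SAP, before outcomes are tabulated, how undetermined events are counted. Counting them as ipsilateral, with a sensitivity analysis excluding them, is cautious for a safety endpoint; another rule is acceptable if fixed in advance.
4. As a minor addition, allow more than one selection in item 5 for these four categories, so that the component rates are complete.

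The cost is SAP wording, one eCRF field and one multiple-selection change. Some queries may be needed, because the protocol does not require source notes to state side. No patients, visits or procedures are added. If the eCRF cannot be changed, items 1 and 3, with a stated source and assessor for side, still settle the definition.
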